3.4.6 Secondary endpoint part 2-f

Blood pressure (pre- and post-dialysis) and its inter-visit variability

Referring to the publication by Rossignol and al. [11], a coefficient of variation for values at each visit time will be calculated and compared between treatment groups (spironolactone vs. placebo). The parameter will be described and compared using the usual statistics.

An alternative method could be performed, conditioned to model hypothesis, to evaluate treatment group effect on blood pressure mean values and variabilities using a Mixed Model for Repeated Measures (MMRM).

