3.1 General issues for statistical analyses

Statistical software

All statistical analyses will be performed using SAS® Software version 9.4 in a Windows environment, or R software version 3.6.3.

Missing data and outliers

All efforts will be made to collect outcome data including in patients withdrawn from the trial for whichever reasons and to minimise the amount of missing data. Unless specifically indicated, missing data will not be replaced. Outliers will be discussed as to whether to be kept or set as missing prior to database lock.

Stratification and centre effect

Unless otherwise specified, the treatment effect will be estimated on the primary and secondary outcomes after adjustment on the stratification variable.

Data transformation

Analysis of continuous variables may require transformation to normalise the distributions if the latter is justified to fulfil the hypotheses of the statistical methods to be used.

Derived and computed variables

Calculated delays since randomisation will be calculated as the time elapsed since the day of randomisation (day zero).

Delays will be converted in years or months by dividing the delays by 365.25 days or 30.4375 days respectively.

Duration=Delay+1 (days)

For the patient's date of birth, if no day is entered then it will all be replaced by 15.

Some derived and computed variables (such as delays) have been initially identified, and are described later in the document. It is expected that additional derived variables may be required. The SAP will not be amended for additional variables that are not related to the primary target or key secondary target variables. Any additional derived or computed variables will be identified and documented in the SAS programs that create analysis files.

Usual statistical presentations and tests

Description of continuous variables includes the mean, standard deviation, median, 1st and 3rd quartile, and range.

Description of categorical variables includes the frequency and percentage (based on non-missing values). Description of ordered variables includes the frequency, percentage and cumulative percentage.

Unless otherwise specified, between-group differences will be tested using the Wilcoxon rank-sum test for quantitative outcomes (or Student's t-test in case of normal distribution), using Fisher's exact test for binary outcomes, and the Mantel-Haenszel Chi-square test for ordinal outcomes.

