3.2 Descriptive analysis

3.2.1 Demographics and baseline characteristics

Patient characteristics at visit V1 and visit V3 (randomisation visit), will be described globally in the run-in population and globally and by treatment group in the ITT and PP populations, using usual descriptive statistics.

Following the CONSORT recommendations, no statistical tests will be performed to compare the studied groups (Moher D, Hopewell S, Schulz KF, Montori V, Gøtzsche PC, Devereaux PJ, et al. CONSORT 2010 Explanation and Elaboration: Updated guidelines for reporting parallel group randomised trials. J Clin Epidemiol. 2010;2010(63):e1–37).

Demographic and baseline characteristics

Age

Sex

Current or past smoking

Diabetes

Dyslipidaemia

Hypertension

Waist circumference

Weight before and after a dialysis session

IMC

Heart rate before and after a dialysis session

Systolic and diastolic blood pressure in lying position before and after a dialysis session, first measurement and mean of second and third values.

Systolic and diastolic blood pressure in standing position before and after a dialysis session, first measurement and mean of second and third values.

History of cardiovascular disease

History of heart failure hospitalisation

EF <40 % at baseline

Left ventricular hypertrophy

History of atrial fibrillation

ECG characteristics AFib, QRS size, Cornell index, paced ...

NB: Centralized ECG results are not available in the frozen database at the time of the SAP finalisation. These variables will be analysed later on.

Disease characteristics

First renal replacement treatment

Renal transplant

Date of first renal replacement treatment

Cause of ESRD:

- Arteriolar nephrosclerosis

- Glomerulonephritis or vascular nephritis
- Diabetes
- Tubulointerstitial nephropathy
- Hereditary or polycystic cause of ESRD
- Other cause of ESRD

Being on a waiting list for renal transplantation

Haemodialysis characteristics

Last measurement of residual diuresis in mL/24h (in the last 3 months)

Weekly frequency of dialysis sessions

Haemodialysis duration

Blood flow

Maximal ultrafiltration rate

Online haemodiafiltration

Potassium concentration in dialysis bath

Calcium concentration in dialysis bath

Type of vascular access

Potassium concentration

Laboratory characteristics

Blood glucose

Calcium level

Phosphorus level

Sodium level

Total cholesterol level

High-density lipoprotein (HDL) level

Triglyceride level

C-reactive protein (CRP) level

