3.2.2 Follow-up data

For ITT and PP populations, follow-up variables will be described by treatment group using usual statistical tests (cf. paragraph 3.1).

Descriptive statistics for visits V2 and V3 to final visit

Weight before and after a dialysis session

Systolic blood pressure in lying position before and after a dialysis session, first measurement and mean of second and third values

Systolic blood pressure in standing position before and after a dialysis session, first measurement and mean of second and third values

Potassium concentration before a dialysis session

Concomitant treatments: ACE inhibitors, ARBs, potassium-sparing diuretic (potassium chelator), loop diuretic, potassium concentration in dialysis bath, or other

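### For blood pressure level (endpoint 2-f), the SAP fixes no baseline-adjusted analysis, although pressure is recorded before randomisation

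*SAP*

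**What the plan says.** Section 3.4.6 names the endpoint as "Blood pressure (pre- and post-dialysis) and its inter-visit variability", so level and variability both belong to it. Its firm analysis is of the coefficient of variation: "The parameter will be described and compared using the usual statistics". The level appears only in the alternative that follows, a model that could be fitted "to evaluate treatment group effect on blood pressure mean values and variabilities using a Mixed Model for Repeated Measures (MMRM". No fixed effects, baseline term, visit structure or covariance are given.

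Level is also compared in section 3.2.2, part of the descriptive analysis: "follow-up variables will be described by treatment group using usual statistical tests (cf. paragraph 3.1". The list there runs from V2 and V3 to the final visit and includes systolic pressure, lying and standing, before and after dialysis. Diastolic pressure is not on it. Section 3.1 defines the tests: "between-group differences will be tested using the Wilcoxon rank-sum test for quantitative outcomes (or Student's t-test in case of normal distribution".

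The general rule on covariates in 3.1 is that "the treatment effect will be estimated on the primary and secondary outcomes after adjustment on the stratification variable". That variable is centre.

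Section 3.2.1 describes patients at V1 and at V3, the randomisation visit, and lists "Systolic and diastolic blood pressure in lying position before and after a dialysis session, first measurement and mean of second and third values", with the same for the standing position.

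**The concern.** A patient's pressure before allocation usually predicts that patient's later pressure. An analysis that ignores it leaves the predictable part of the between-patient spread in the error term, and any chance difference between arms at randomisation stays in the estimate. Confidence intervals are then wider than the data require. Section 3.1 says that intervals not adjusted for multiplicity are to be read as a measure of precision, and precision is what is lost here. Because the MMRM is optional and has no stated terms, the choice to fit it, and to include baseline, is also left open.

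**Working it through.** **Which analyses of level exist, and can they use baseline?**

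| Source | Status | Pressure covered | Baseline used? |
|---|---|---|---|
| 3.2.2 with 3.1, Wilcoxon or t-test | firm, in the descriptive section | systolic only | no; these tests carry no covariate, not even centre |
| 3.4.6, coefficient of variation | firm | variability, not level | not relevant to level |
| 3.4.6, MMRM | optional | means, pre- and post-dialysis | not stated |
| 3.1, default adjustment | general rule | all secondary outcomes | no; centre only |

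No planned analysis commits to a baseline term, and no change from baseline is defined for blood pressure.

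**Is the covariate valid?** V1 precedes the run-in. V3 follows one month of open-label run-in drug in all patients (section 1.3.1). Both readings precede the effect of allocation, so either may be a covariate, but they are taken under different conditions.

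**The plan's own figure.** The SAP gives no sample size, SD, correlation or power for blood pressure. Its only size figure is 750 (375 per arm) for the primary endpoint, which reproduces:
- Hazards: -ln(1 - 0.18) = 0.1985 and -ln(1 - 0.126) = 0.1347, so HR = 0.679.
- Two-year event probabilities: 1 - 0.82^2 = 0.328 and 1 - 0.874^2 = 0.236, mean 0.282.
- Schoenfeld: 209 events, 209/0.282 = about 741 patients. Freedman: 215 events, about 763 patients.

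I therefore use 375 per arm below.

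**Gain from adjustment, one follow-up value.** Let rho be the correlation between baseline and follow-up, with equal variances.
- Variance ratio = 1 - rho^2, so the variance falls by rho^2.
- Interval width ratio = sqrt(1 - rho^2).
- Equivalent unadjusted size = 750/(1 - rho^2).
- Power for a difference with 80% power unadjusted, which is 2.8016 x sqrt(2/375) = 0.205 SD: Phi(2.8016/sqrt(1 - rho^2) - 1.96).

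| Assumed rho | Variance falls by | Interval narrower by | 750 patients count as | 80% power becomes |
|---|---|---|---|---|
| 0.3 | 9% | 5% | 824 | 84% |
| 0.4 | 16% | 8% | 893 | 86% |
| 0.5 | 25% | 13% | 1000 | 90% |
| 0.6 | 36% | 20% | 1172 | 94% |
| 0.7 | 49% | 29% | 1471 | 97.5% |

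**Mean of eight follow-up visits** (V6 to V13), assuming compound symmetry. With v = (1 + 7 rho)/8, the variance ratio is (v - rho^2)/v. At rho = 0.5, v = 0.5625 and the ratio is 0.3125/0.5625 = 0.556, a fall of 44%. At rho 0.3 and 0.7 the falls are 23% and 66%.

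The direction does not depend on the assumed rho: at this sample size, any correlation that is not negligible gives a gain.

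**The case against.** **The SAP does not exclude baseline.** A reader might infer that the MMRM was specified without it. The text does not support that, because 3.4.6 lists no terms at all. The optional potassium MMRM in 3.4.7 sits under an item running from V1 to V5, so pre-randomisation values may have been meant to enter the response. A blood pressure model built that way could recover much of the same precision. This objection stands: the gap is an omission. It does not close the gap, since the model is optional and nothing says baseline will enter.

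**The per-visit tests are not declared to be the analysis of 2-f.** They sit in a descriptive section and cover systolic pressure only, and the usual statistics in 3.4.6 refer to the coefficient of variation. This stands too. What remains is that they are the only firm comparisons of level.

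**Calling the plan unadjusted would go too far.** Section 3.1 adjusts for centre by default. What is missing is adjustment for baseline.

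**The size is assumed.** It would be wrong to read the table as the trial's power for blood pressure, because no effect on it was planned. High variability between visits would lower rho, and at 0.3 the gain in power is only about 4 points. The patient equivalents assume that all 750 contribute a value, whereas death, transplantation and drop-out will reduce that number.

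**The endpoint is for hypothesis generation** (section 1.2) and lies outside the testing hierarchy. This limits the weight of the point but is no reason to forgo precision that costs almost nothing.

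**Conclusion.** The point holds as a cheap improvement of low severity. For blood pressure level, the SAP commits to no analysis that uses the recorded pre-randomisation value. Adjustment would cut the variance of a single-visit comparison by 9% to 49% for rho between 0.3 and 0.7, and by 25% at 0.5. These figures rest on an assumed correlation and equal variances. If centre is also in the model, rho is the correlation within centres.

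The loss is one of precision. Randomisation keeps the unadjusted comparison unbiased, the type I error is not affected, and the primary result is untouched. The point does not extend to the coefficient of variation or to the quality-of-life models.

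**What to change.** In section 3.4.6, make the MMRM the planned analysis of blood pressure level:
- **Response:** post-randomisation visits only.
- **Terms:** treatment, visit, treatment-by-visit, centre as grouped for the primary analysis, baseline, and baseline-by-visit.
- **Baseline:** the V3 reading, stated to be before allocation and after one month of open-label run-in drug.
- **Missing V3:** a simple baseline imputation, which V1 may inform. Do not put the V1 value directly in its place, because that mixes pre-drug and on-drug readings in one covariate. Section 3.1 replaces no missing data unless this is indicated, so the exception must be written down.
- **Separate models:** systolic and diastolic, before and after dialysis, each with one pre-stated position (lying or standing) and one pre-stated reading (the first, or the mean of the second and third).
- **Report:** adjusted mean differences with 95% CI. Keep the per-visit summaries of 3.2.2 as description only.

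The cost is SAP wording and one covariate already collected. The small downside is that a few baseline values may need imputation.

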3.4.7 Secondary endpoint and part 2-h

- incidence of hyperkalaemia > 6 mmol/L (Diagnostic or MedDRA codage, EI_date (Table EI) with DIAGNOSTIC='7' (hyperkaliemie >6 mmol/l) and EI_GRAVE=1 or LLT containing ('HYPERKALEAMIA' and EI_GRAVE=1), as
 - i. reported anytime and with any method during follow up (Time to first and recurrent)
 - ii. reported at per protocol scheduled visits (Time to first and recurrent)

The incidence and number of each event will be described and compared using the usual statistics.

Sensitive analysis of serum potassium could be considered:

- incidence of hyperkalaemia \geq 5.5 mmol/L, as
 - i. reported anytime and with any method during follow up (Time to first and recurrent)
 - ii. reported at per protocol scheduled visits (Time to first and recurrent)
- Serial changes and variability of serum potassium at scheduled per-protocol visits over time (visit V1 to visit V5)
For the analysis of longitudinal data for serum potassium values, summary parameters (auc, means, etc.) could be estimated and compared between treatment groups. A mixed model for repeated measures (MMRM) could be performed to estimate marginal means and variabilities.
- incidence of hypokalaemia at <4 mmol/L and <3.5 mmol/L, as
 - i. reported anytime and with any method during follow up (Time to first and recurrent)
 - ii. reported at per protocol scheduled visits (Time to first and recurrent)

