1.2 Secondary objectives

Part1

Following a hierarchical strategy of statistical tests including the primary endpoint, the secondary objective is to determine the effects of spironolactone versus placebo on the composite win ratio endpoint of: 1. all-cause mortality; 2. time to cardiovascular event (hospitalisation for heart failure, or non-fatal myocardial infarction, or non-fatal acute coronary syndrome or stroke) at 2 years using the Finkelstein and Schoenfeld method.

Part2

Additional secondary objectives will be considered for hypothesis generation:

- a) mortality rate from non-CV causes
- b) the cumulative rates of the composite outcome of non-fatal primary outcome events (hospitalisation for heart failure or non-fatal MI or acute coronary syndrome or stroke) and occurrence of
 - i. All-cause death from any cause,
 - ii. CV death
 - iii. non-CV cause
- c) cardiovascular event-free survival: survival without non-fatal MI and acute coronary syndrome, hospitalisation for heart failure, non-fatal stroke, or resuscitated cardiac arrest
- d) incidence of procedures related to stenosis or thrombosis of the vascular access for HD
- e) incidence of coronary or peripheral revascularisation (including lower-limb amputations)

- f) blood pressure (pre- and post-dialysis) and its inter-visit variability [Rossignol P, Cridlig J, Lehert P, Kessler M, Zannad F. Visit-to-visit blood pressure variability is a strong predictor of cardiovascular events in hemodialysis: insights from FOSIDIAL. Hypertension. 2012 Aug; 60(2):339-46. doi: 10.1161/HYPERTENSIONAHA.111.190397. Epub 2012 Jul 9.]
- g) Occurrence of complete arrhythmia by atrial fibrillation.
- h) incidence of hyperkalaemia > 6 mmol/l;

The following objectives and ancillary studies will be analysed in dedicated SAP:

- i) *estimation of the effect of treatment on the quality of life of patients with this dual pathology: CKD in HD and established cardiovascular pathology,*

Part3: Ancillary studies

- j) *Creation of a biological collection for subsequent biomarker studies (serum and DNA libraries),*
- k) *Post-study, mortality and cardiovascular morbidity assessed 3, 5 and 10 years after the end of the double-blind follow-up period, by consulting national epidemiological registers.*

A health economics ancillary study will complete this project.

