1.3 Experimental design and studied population

1.3.1 Study outline

This is a randomised, controlled, double-blind, multicentre, parallel-group trial. After an open-label run-in period of one month under 25 mg spironolactone every second day (administered in practice after the HD session, three times a week), patients was randomised (spironolactone vs. placebo), and undergo titration over one month, with a maximum single dose of 25 mg/day. A pre-specified algorithm for the management of the risk of incident hyperkalaemia was followed, including dose adjustments, temporary discontinuation of the study treatment, in addition to the usual dietary measures, and the use of chelating resins and low-potassium dialysis baths.

Serum potassium levels was measured at the beginning of each session (3 times per week) over 2 months, and thereafter according to the titration algorithm data (in addition to usual follow-up, including serum potassium monitoring every two weeks), and during each visit of the protocol. Patients was followed for 2 years on average.

A Steering Committee (chaired by the coordinator, and comprised of nephrologists, cardiologists, pharmacologists, a statistician methodologist), an Oversight Committee and a Critical Events Adjudication Committee was planned.

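### Endpoint 2-h is labelled as all hyperkalaemia above 6 mmol/L, but its rule counts only adverse events flagged EI_GRAVE=1, and its text-search branch is faulty

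*SAP*

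**What the plan says.** Section 1.2 lists objective 2-h as the "incidence of hyperkalaemia > 6 mmol/l". It is one of the additional objectives kept for hypothesis generation.

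Section 3.4.7 sets two versions: (i) events "reported anytime and with any method during follow up (Time to first and recurrent"), and (ii) events reported at the scheduled visits. Incidence and number are to be described and compared between arms.

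The rule that identifies an event draws on Table EI, the adverse-event table: "DIAGNOSTIC='7' (hyperkaliemie >6 mmol/l) and EI_GRAVE=1 or LLT containing ('HYPERKALEAMIA' and EI_GRAVE=1"). It has two branches joined by an or:

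- a coded branch, on diagnosis code 7;
- a text branch, on the LLT.

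The same section then lists optional analyses, one of which is "Serial changes and variability of serum potassium at scheduled per-protocol visits over time (visit V1 to visit V5"), with a possible repeated-measures model. Section 1.3.1 states that potassium continues to be measured, "including serum potassium monitoring every two weeks), and during each visit of the protocol". Section 3.2.2 includes "Potassium concentration before a dialysis session" among the variables described by arm up to the final visit.

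**The concern.** A laboratory endpoint has been given a seriousness filter that its objective does not contain. A value above 6 mmol/L found at a scheduled visit and handled without being declared a serious event meets the objective but not the rule. The resulting rate would depend on reporting and hospitalisation habits as well as on potassium.

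The label matters here. Section 1 says that clinicians hold back from this drug class because of hyperkalaemia, and it names safety as an aim of the study. A serious-only count published as the incidence of hyperkalaemia above 6 mmol/L would be mislabelled and could only be equal to or lower than the quantity named. Version (ii) is affected most, because a scheduled-visit incidence calls for measured values and the rule consults none.

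**Working it through.** The plan gives no figure for this endpoint, so there is none to reproduce. I set the definition against the rule, test the search string, illustrate the effect of the filter, and measure the potassium window.

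**1. Definition against rule.** Written out, the rule is (code 7 AND EI_GRAVE=1) OR (LLT contains the string AND EI_GRAVE=1). EI_GRAVE=1 is therefore necessary for any event to count.

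| Situation | Meets objective 2-h? | Counted by the rule? |
|---|---|---|
| Potassium above 6 recorded, no adverse event reported | Yes | No |
| Potassium above 6, code-7 event, not flagged | Yes | No |
| Potassium above 6, code-7 event, flagged | Yes | Yes |
| Potassium above 6, flagged event identifiable only by LLT | Yes | No (string fails) |
| Potassium 6 or below, flagged event, LLT branch respelled only | No | Yes |

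Section 3.5.1 cites Table EI as the source for all adverse events and for serious ones, so the flag can act as a real filter. Section 3.4.5 takes endpoints 2-d, 2-e and 2-g from the same table without it.

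**2. Search string.** The SAP string is HYPERKALEAMIA. A literal substring test gives:

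- in HYPERKALAEMIA: false (the E and the A are transposed);
- in HYPERKALEMIA: false;
- in HYPERKALIEMIE: false.

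Taken literally, the text branch finds none of these spellings. The coded branch is unaffected.

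**3. Illustration of the filter.** Inputs: n = 375 per arm (section 1.3.4). The true rates p0 and p1, and the share s of events flagged serious, are assumptions; s is taken as equal in both arms.

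- Counted rates: s·p0 and s·p1.
- Counted difference: s·(p1 − p0).
- Power = Φ{[d − 1.96·√(2·p̄(1−p̄)/n)] / √[(a(1−a) + b(1−b))/n]}, with a = s·p0, b = s·p1, d = b − a and p̄ = (a+b)/2.

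Worked case, 10% against 18% with s = 0.5: a = 0.05, b = 0.09, p̄ = 0.07. Null standard error √(2×0.07×0.93/375) = 0.01863; alternative standard error √[(0.0475+0.0819)/375] = 0.01858. (0.04 − 1.96×0.01863)/0.01858 = 0.19, so power is 0.574.

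| s | 10% vs 18%: difference, power | 20% vs 30%: difference, power |
|---|---|---|
| 1 | 8.0 points, 0.886 | 10.0 points, 0.887 |
| 0.75 | 6.0 points, 0.765 | 7.5 points, 0.750 |
| 0.5 | 4.0 points, 0.574 | 5.0 points, 0.544 |
| 0.25 | 2.0 points, 0.319 | 2.5 points, 0.292 |
| 0.1 | 0.8 points, 0.152 | 1.0 points, 0.139 |

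This is a normal approximation; section 3.1 names Fisher's exact test for binary outcomes. The table shows only how the absolute difference scales with s. With s equal in both arms the risk ratio is unchanged.

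**4. Window of the optional serial analysis.** The visit table in section 1.3.5 puts V5 at week 4 and marks blood potassium at V6 to V13 (months 3 to 24). V1 to V3 are run-in and randomisation. The window thus holds 2 of the 10 post-randomisation visits V4 to V13, and 28/730.5 = 3.8% of two years. Both figures are approximate: two years is an average, and a footnote to that table mentions V17 and V21.

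**The case against.** The strongest reply is that the plan looks at hyperkalaemia elsewhere and that 2-h carries little inferential weight.

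- **Other coverage.** Section 3.5.2 lists hyperkalaemia, and hospitalisation for it, among the adverse events of special interest, described by arm for all adverse events without a seriousness filter. Section 3.2.2 describes potassium by arm to the final visit. Section 3.4.7 adds optional analyses at 5.5 mmol/L and above, again unfiltered. This stands as a limit on the damage, and it is why one should not infer that the drug's main risk is under-counted across the plan. It does not cure 2-h: section 3.5.2 has no 6 mmol/L threshold and no tests, and section 3.2.2 concerns concentration, not the incidence of values above 6.
- **The misspelling.** A reader might infer that the endpoint depends on a term that matches nothing. It does not: the coded branch works alone, and what is lost is serious events identifiable only by LLT. The error may also be corrected in programming. The missing threshold would remain.
- **The V1 to V5 window.** A reader might infer that potassium is not examined after week 4. Only one optional analysis stops there, and it covers the titration period, when sampling is densest. Extending it is an improvement, not the correction of an error.
- **What Table EI holds.** The visit schedule has a row for serious adverse events and none for others. If few non-serious events were recorded, removing the flag would change little. But values above 6 without a serious event would still be missed, so the case for using the measured values becomes stronger.

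**Conclusion.** The point holds for endpoint 2-h. As written, section 3.4.7 would give a serious-only count under a label, and with a declared scope, that promise all hyperkalaemia above 6 mmol/L. The text branch is wrong twice: the string fails, and if it is only respelled, it admits events at or below the threshold.

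The size is unknown, because the SAP does not give the share of values above 6 mmol/L that were declared serious. The power figures rest on assumed rates and shares and are not evidence of actual impact. The conclusion also assumes that EI_GRAVE=1 means serious, which the French word supports but no code list confirms.

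This should be fixed, but it is not critical to the trial. Objective 2-h is hypothesis-generating and stands outside the hierarchy of section 3.4.1. The primary endpoint and the win ratio are untouched.

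**What to change.** In section 3.4.7:

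1. Derive 2-h from recorded serum potassium above 6 mmol/L: scheduled-visit values for version (ii), any recorded value for version (i). Add code-7 adverse events regardless of EI_GRAVE to version (i), and to version (ii) where they arise at a scheduled visit.
2. Report serious hyperkalaemia (EI_GRAVE=1) as a separate, labelled subset, and state the meaning of the code.
3. Correct the LLT term to cover HYPERKALAEMIA and HYPERKALEMIA. Use it only for the serious subset, or together with a recorded value above 6 mmol/L.
4. As a minor improvement, run the optional serial and repeated-measures potassium analysis on all scheduled post-randomisation visits from V4, not only to V5.

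The cost is SAP wording and reprogramming. Scheduled-visit potassium should already be in the database, since section 3.2.2 plans to describe it. The SAP does not say whether the routine two-weekly results were entered, so version (i) should state which values were available. If 2-h has already been analysed under the current rule, report both counts and explain the change.

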1.3.5 Chronological sequence

Eligible patients having signed the consent form participate in the one-month run-in phase after which they were randomised conditional to the absence of hyperkalaemia ≥ 5.5 mmol/l on two occasions or on the day of randomisation or of serious adverse events.

The included and randomised patients participate in the study for a duration of 2 years on average, the latter of which can be amended by the Steering Committee in light of the rate of event occurrences. The study was completed when the number of incidents necessary for attaining a sufficient power has been observed. Blinding was lifted only in the case of a serious adverse event in which care management may be modified according to the treatment received by the patient: spironolactone/placebo; patients were followed until the end of the study.

Figure 1: Scheme of the study

Figure 1: ALCHEMIST trial design

(*): dosage of 25 mg/eod; patients presenting blood potassium > 5.5 mmol/l on two occasions will be excluded before randomization;
 (**): maximum dosage of 25 mg/d; could be reduced or temporarily suspended if blood potassium is > 5.5 mmol/l;
 From V1 to V12: Other visits will be scheduled if blood potassium is > 5.5 mmol/l.

Summary table of visits.

	Visit 1 W-4	Visit 2 W-2	Visit 3 D0	Visit 4 W+2	Visit 5 W+4	Visit 6 à 13 M3 to M24
Verification of the selection criteria	x					
Verification of the inclusion/exclusion criteria						
Pregnancy test (if applicable)	x					
Information/Informed consent	x					
Physical examination	x	x	x	x	x	x
ECG	x					
Dispensing of medication	x		x		x	x
Self-questionnaires on quality of life	x					x (**)
Randomisation			x			
Blood potassium	3/week	3/week	3/week	3/week	x	x
Verification of compliance		x	x	x	x	x
Dosage increase		x	x	x	x	x
Dosage adjustment (if necessary)				x	x	x
Concomitant treatments	x					x
SAEs		x	x	x	x	x

(**) only at V6, V9, V13, V17 and V21

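### The optional serial potassium comparison in SAP 3.4.7 runs from V1 to V5, but V1 to V3 precede randomised treatment, so a pooled mean is diluted and an AUC only gains noise

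*SAP*

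**What the plan says.** SAP 3.4.7 introduces a group of further potassium analyses with "Sensitive analysis of serum potassium could be considered". One of them is "Serial changes and variability of serum potassium at scheduled per-protocol visits over time (visit V1 to visit V5"). For these longitudinal values, "summary parameters (auc, means, etc.) could be estimated and compared between treatment groups"; a mixed model for repeated measures is named as another option. The section names no baseline visit and does not say which visits carry the comparison between arms.

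The visit table in 1.3.5 gives V1 at W-4, V2 at W-2, V3 at D0 (randomisation), V4 at W+2 and V5 at W+4. Patients "participate in the one-month run-in phase after which they were randomised", and 1.3.1 describes the sequence as "After an open-label run-in period of one month under 25 mg spironolactone every second day", followed by randomisation.

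Elsewhere the plan treats the early visits as baseline. In 3.2.1, "Patient characteristics at visit V1 and visit V3 (randomisation visit), will be described globally in the run-in population" and, by arm, in the ITT and PP populations. Potassium concentration is on the list, and "no statistical tests will be performed to compare the studied groups". In 3.2.2, "follow-up variables will be described by treatment group using usual statistical tests (cf. paragraph 3.1"); pre-dialysis potassium is listed there for V2 and V3 through to the final visit.

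**The concern.** Up to and including V3, every patient has been on the same open-label drug and none has taken randomised treatment. Expected arm differences at V1, V2 and V3 are therefore zero. A summary that pools these visits with V4 and V5, and is then compared between arms, mixes three values that carry no treatment contrast with two that do. It also brings into a compared outcome values on which 3.2.1 declines to test the arms.

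Potassium is the main safety worry with this drug in this population, and dilution or added noise makes a real potassium effect look smaller or less certain. A pooled result under 3.4.7 could also seem to disagree with the by-visit comparison under 3.2.2 when the only difference is the window.

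**Working it through.** The SAP states no effect size, SD or power for this analysis, so there is no figure of its own to reproduce.

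**Inputs from the SAP.** Visit times -4, -2, 0, +2, +4 weeks (1.3.5); same open-label treatment for all before randomisation (1.3.1); 375 per arm as planned (1.3.4).

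**1. Expected arm differences at V1 to V5.** (0, 0, 0, d4, d5), or (0, 0, 0, d, d) if constant after randomisation.

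**2. Equal-weight mean.** (d4 + d5)/5 = 0.40 × (d4 + d5)/2. The factor 0.40 holds for any d4 and d5.

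**3. Trapezoid AUC, two-week spacing.**
- V1-V5, weights (1, 2, 2, 2, 1): 2·d4 + d5 = 3d.
- V3-V5, weights (0, 0, 1, 2, 1): 2·d4 + d5 = 3d.
- The V1-V3 segment adds no expected difference. Divided by its length, the AUC shows 3d/8 = 0.375d over V1-V5 and 3d/4 = 0.75d over V3-V5.

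**4. Noise and power.** Assumed, not in the SAP: SD 0.7 mmol/L, equal correlation 0.5 between visits, d = 0.2 mmol/L, two-sided 5%. For weights w, the variance factor is 0.5·Σw² + 0.5·(Σw)², and √(2/375) = 0.0730.

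| Summary | Arm difference | Variance factor | z | Power |
|---|---|---|---|---|
| Mean, five visits | 0.08 | 0.60 | 0.08/(0.7·√0.60·0.0730) = 2.02 | 52% |
| Mean, V4-V5 | 0.20 | 0.75 | 0.20/(0.7·√0.75·0.0730) = 4.52 | 99% |
| AUC, V1-V5 | 0.60 | 39 | 0.60/(0.7·√39·0.0730) = 1.88 | 47% |
| AUC, V3-V5 | 0.60 | 11 | 0.60/(0.7·√11·0.0730) = 3.54 | 94% |
| AUC, V3-V5, adjusted for V3 | 0.60 | 11 - 2.5² = 4.75 | 5.39 | >99% |
| Mean, V4-V5, adjusted for V3 | 0.20 | 0.75 - 0.5² = 0.50 | 5.53 | >99% |

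**5. Range.**
- SD 0.6 to 0.8 and correlation 0.3 to 0.7, d = 0.2: V1-V5 AUC 31-72%, V3-V5 AUC 81% to over 99%; five-visit mean 35-79%, V4-V5 mean 96% or more.
- d = 0.1 with SD 0.7 and correlation 0.5: AUC 16% against 42%; mean 17% against 62%.
- For correlations from 0 to 0.9 (equal or first-order autoregressive), the V1-V5 AUC has a standard error 1.53 to 1.98 times that of the V3-V5 AUC.

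**6. Within-patient variability over V1-V5.** Let s be the potassium shift in run-in. Assume V1 is off drug and placebo patients are washed out by V4. The mean patterns have these sample variances:
- placebo (0, s, s, 0, 0): 0.30s²;
- spironolactone (0, s, s, s, s): 0.20s²;
- spironolactone if daily dosing doubles the effect (0, s, s, 2s, 2s): 0.70s².

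With s = 0.2 and within-patient variance 0.7² × 0.5 = 0.245, placebo has 0.257 and spironolactone 0.253 (-1.6%) or 0.273 (+6.2%). Over V4-V5 alone all three patterns contribute zero. Variability is therefore little affected, but what difference there is partly reflects the run-in.

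**The case against.** The strongest reply is that 3.4.7 does not prescribe the diluted summary. Means could be means per visit, serial changes could be changes from a baseline visit, and a mixed model read at V4 and V5 would not be diluted. That is correct, and the 0.40 applies only to a mean pooled over the stated window. But 3.4.7 states that window, offers AUCs and means first, and does not say which visits carry the arm contrast.

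Second, V1-V5 has a sensible purpose: it follows patients from the start of run-in through titration, and a longitudinal profile commonly includes pre-randomisation visits. The ban on testing in 3.2.1 concerns baseline tables and does not keep baseline values out of a longitudinal model. This also stands as far as description goes. It does not justify averaging those visits into a between-arm outcome.

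Third, the power figures use values the SAP does not give, and a constant d is doubtful when the dose is raised after randomisation and reduced at potassium of 5.5 mmol/L or more. The absolute powers are therefore illustrative. The 0.40 and the equality of the two AUC contrasts need neither an SD nor a constant d, and the ordering holds at every setting tried.

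Last, little hangs on it. The analysis is optional, its endpoint group is hypothesis-generating, 3.2.2 gives potassium by arm to the final visit, and hyperkalaemia is reported separately in 3.4.7 and 3.5.2. That is accepted and sets the rating.

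**Conclusion.** The point holds, at low importance. If the V1-V5 window is used as written for a pooled mean, the arm difference shrinks to 0.40 of its V4-V5 value. If it is used for a raw AUC, the expected difference equals that from V3 and the standard error is 1.53 to 1.98 times as large, assuming non-negative correlation between visits. Under the illustrative assumptions this roughly halves power. By-visit means, a by-visit mixed model and analyses using V3 as a covariate are not affected, and the effect on variability is small. No primary, hierarchical or main safety conclusion depends on this analysis. It is a worthwhile improvement at almost no cost, not a defect that must be corrected.

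**What to change.** In 3.4.7, for comparisons between arms only:

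- Take potassium at V4 and later visits as the outcome, with V3 potassium as baseline covariate.
- Fit the mixed model with a treatment-by-visit term and report the arm difference at each visit.
- Start any AUC at V3 and adjust it for the V3 value.
- Compute between-arm variability on post-randomisation visits only. Include visits after V5, since V4 and V5 alone give one difference per patient.
- Keep V1 to V3 potassium as a description of the run-in population, without comparing arms.

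The cost is SAP wording. Potassium from V3 to the final visit is already listed in 3.2.2, so no new data are needed.
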